1.2.10 Clinical Experience with Single Agent rhIL-15 in the Treatment of Cancer

1.2.10.1 First in Human Intravenous Bolus (IVB) trial

The first in-human (FIH) phase I trial of rhIL-15 administered the treatment as rapid (30 minute) IV bolus (IVB) to adults with refractory metastatic malignant melanoma and metastatic renal cell cancer [70].-This study was initially planned with a starting dose of 3 mcg/kg/day given for 12 consecutive days. However, after the first patient treated developed grade 3 hypotension and after patient #5 at this dose level developed grade 3 thrombocytopenia, the protocol was amended to add the two lower doses of 1.0 and 0.3 mcg/kg/day with the expectation of returning to higher dose levels later. When two of four patients treated at the 1.0 mcg/kg/day dose unexpectedly developed asymptomatic grade 3 alanine aminotransferase (ALT) and aspartate aminotransferase (AST) elevations that were dose limiting, all subsequent patients were treated at the 0.3 mcg/kg dose level. All 9 patients with IL-15 at 0.3 mcg/kg/day received 12 doses without a DLT, and the maximum tolerated dose (MTD) of rhIL-15 was defined as 0.3 mcg/kg/day.

There was a consistent temporal pattern of post-treatment adverse events in patients receiving 3 mcg/kg/day doses of IL-15 with fever and rigors beginning 2 ½ to 4 hours following the start of IV infusions, soon after drops in blood pressure were seen with nadirs approximately 20 mm/Hg below pretreatment levels that responded slowly to rapid normal saline (NS) infusions. These physiologic changes were concurrent with an up to 50-fold elevation of serum IL-6 and interferon gamma (IFN γ) levels. Flow cytometry of peripheral blood lymphocytes in patients receiving 3 mcg/kg/day revealed a dramatic efflux of NK and memory CD8 T-cells from the circulation within minutes of IL-15 administration, gradual rise in NK cell numbers in the first 4 to 5 days of treatment, followed by an influx and hyperproliferation yielding a 10-fold expansion in the number of NK cells at the end of or after completion of the treatment cycle. A modest increase in the number of CD8 $^{+}$ T-cells was also seen but virtually all of these CD8 $^{+}$ T-cells were activated and expressed high levels of Ki67, CD38 and HLA-DR. In this first-in-human phase I trial there were no clinical responses with stable disease as the best response. However, 5 patients had decreases of between 10% and 30% of their marker lesions that included 2 patients that cleared their lung lesions.

1.2.10.2 Subsequent Clinical Trials with Subcutaneous (SC) or Continuous Intravenous (CIV) rhIL-15

The clinical toxicities that limited dose escalation in the IVB trial were associated with intense cytokine production within the first few hours of treatment and marked by exceedingly high IL-15 levels. Serum IL-15 concentrations at these levels would be sufficient to signal through the intermediate affinity (IL-2) IL-15R β and gamma chain (γ c) receptor pair that resulted in the undesirable toxicities seen in the FIH trial and suggested that dosing strategies that limited the C_{max} , increased the duration of lower IL-15 levels that were optimal for high-affinity IL-15 $\alpha\beta\gamma$ receptor would improve the IL-15 stimulatory signal [71]. Alternative SC and CIV dosing regimens were evaluated first in non-human primate (NHP) rhesus macaques and subsequently in phase I clinical trials. The preclinical NHP experiments assessed the pharmacokinetics (PK) for multiple dose levels including the 20 mcg/kg dose given as an IVB (C_{max} 720 pg/mL) and produced more advantageous IL-15 concentration; C_{max} of 50 pg/mL for SC injections and C_{max} of 4 pg/mL for CIV infusion with more balanced PK parameters that stimulated greater expansion of NK and CD8 $^{+}$ effector cells [67-69].

A phase I dose escalation trial (Clinical Trials Identifier: NCT01727076) performed in adults with refractory metastatic solid tumors that assessed a SC rhIL-15 treatment regimen (Monday-Friday for 2 consecutive weeks of a 4-week cycle) was performed under the direction of Cancer Immunotherapy Trials Network (CITN) at dose levels of 0.25, 0.5, 1, 2 and 3 mcg/kg/day[71]. Nineteen patients were treated with 14 patients receiving \geq 2 cycles of treatment. Patients experienced common cytokine side effects of fevers, chills, fatigue, mild anorexia, transient biochemical laboratory abnormalities and transient lymphopenia. The MTD was 2 mcg/kg/day; with notable serious adverse events of pancreatitis at the 2.0 mcg/kg dose level and grade 3 cardiac chest pain at the 3mcg/kg dose level. Flow-cytometry data demonstrated $>$ 10-fold increase in NK cells, an approximately 3-fold increase in CD8 cells at the 2 highest dose levels and a dramatic increase in the frequency of CD56^{bright} CD3^{negative} NK cells that peaked about 3 days after the last injection on day 15 of the treatment cycle. Again, stable disease was the best response, but 1 patient remained on treatment for 2 years without progression but relapsed soon after the rhIL-15 was stopped. This protocol defined a safe immunostimulatory regimen that could be given as an outpatient in future combination treatment protocols [71].

A parallel phase I dose escalation trial (Clinical Trials Identifier NCT01572493) was performed in adults with refractory metastatic cancers the Clinical Center NIH, rhIL-15 was administered to patients with metastatic malignancy by CIV for 10 days at progressively increasing doses to 3 patients each of 0.25, 0.5, 1.0, 2.0 and 4.0 mcg/kg/day. Two dose-limiting toxicities were observed at 4.0 mcg/kg/day, one hepatotoxicity and the other visceral arterial ischemia making 2 mcg/kg the MTD that was well tolerated in the 9 patients treated at this dose [72]. The PK data from the CIV regimen was notably different from the IVB regimen having an appreciably lower C_{max} 5662 pg/mL (2 mcg/kg cohort) compared to 30,420 pg/mL (for 3 mcg/kg cohort). The serum IL-15 level was largely maintained in the CIVrhIL-15 treated patients over the first 48 hours compared to the rapid decline seen in the IVB patients with serum half-life of approximately 2 $\frac{1}{2}$ hours. Patients in the CIV trial showed a much lower serum IL-15 level during the last 2 to 3 days of the infusion that was approximately 10% of their C_{max} level. which is believed to be related to the high number of high affinity IL-15 receptor bearing effector cells acting as a sink rapidly binding and clearing the free serum IL-15. More limited PK data from the SC treatment protocol showed fairly comparable C_{max} 6480 pg/mL (for 3 mcg/kg cohort) 4 hours after injection that is largely gone by

24 hours post injection. As predicted in the NHP toxicology studies the lower but sustained IL-15 levels produced by the SC and CIV regimens produced the large increase in activated effector cells at the higher dose levels in the respective trials

The CIV regimen produced characteristic changes in lymphocyte numbers with early lymphopenia (days 1 to 3) for both T and NK cells, followed by a gradual increase in cell numbers and dramatic rise in cells (30 to 80-fold increase in NK cells, 2 to 6-fold increase in CD8⁺ cells and 350-fold increase in CD56^{bright} NK cells) during the 48 hours after completion of the treatment as shown below in Figure 3⁽⁷⁷⁾. The rate of proliferation of different subsets of NK cells assessed by Ki67 was consistent with their levels of CD122 (IL-2/IL-15R β) expression with CD56^{bright} > CD56^{dim}, CD94^{high}, > CD56^{dim}, CD94^{low}. The functional capacity of the dominant CD56^{bright} subset was augmented following IL-15 administration and was associated with an increase in their expression of perforin and granzyme. Although the specific lytic activity of CD56^{bright} cells was not as great as that of CD56^{dim} cells, their single cell lytic and antibody-dependent cellular cytotoxicity (ADCC) activity were markedly increased by rhIL-15 treatment. This ADCC activity was confirmed in assays with anti-CD20 antibody coated Raji cells, natural cytotoxicity to K562 cells, mediated by NKp30 and NKp46 as well as by MICA/NKG2D-mediated cytotoxicity [73]. These clinical trial results and preclinical data combining ICI, anti-CTLA4 and anti-PD1, with rhIL-15 [74, 75] and antitumor antibodies promote the development of clinical trials with these combinations [76].

The CIVrhIL-15 trial was subsequently amended to evaluate a 5-day (120 hour) regimen with further dose escalation at 3, 4 and 5 mcg/kg/day. Ten additional patients have been safely treated at these dose levels without DLTs or remarkable toxicities. Common adverse events (AEs) as expected have been the fatigue, fevers, chills or occasional rigors, capillary leak syndrome and reversible laboratory abnormalities. As seen in table 2, this 5-day regimen has produced impressive increases in absolute lymphocyte count (maximum ALC 25,000 to 30,000 cells/mL, NK cells (30 to > 80-fold increase) and CD8 cells (5 to 8-fold increase) that generally has been higher than seen in the patients treated at the 2 mcg/kg dose level for 10 days.

[figure not shown]

laboratory abnormalities include early (treatment days 1-4) leukopenia, lymphopenia, thrombocytopenia, transaminitis, anemia, hypoalbuminemia during the whole treatment cycle, late cycle rises in bilirubin in patients treated with doses ≥ 2 mcg/kg and the dramatic spike in lymphocytes that occurs in the 72 hours after completion of the CIV infusion. The norm is for most of these laboratory abnormalities to begin returning or to resolve to baseline while treatment continues. There has been no evidence of increased risk of infection or requirement for antibiotic treatment during the period of cytopenias or increased bleeding during the period of decreased platelets. Decreases in hemoglobin (Hgb), which most likely is related to increased sequestration of red blood cells in the liver and spleen, generally require more time to return to pretreatment levels. This incidence of anemia has possibly been greater in the patients treated with the 5-day regimen and the 3, 4 or 5 mcg/kg dose levels, but this assessment has been complicated by the fact that 8 of the 10 patients treated in these dosing cohorts have GI malignancies and were found to be iron deficient. Some patients were transfused during their 2nd or later cycle of treatment and those who tolerated oral iron replacement therapy had replenishment of their iron stores to improve their Hgb level. A number of the patients previously treated in the rhIL-15 trials had past history of autoimmune phenomena related to their prior cancer treatment with checkpoint inhibitors and none of these patients developed new or recurrent autoimmune toxicities.

As seen in **Figure 4**, the rate and severity of irAEs is also generally lower for anti-PD-L1 agents [77], including avelumab (**Table 4**), with the onset of the clinical events of greatest concern occurring generally 2 to 3 months after initiation of treatment. Avelumab has been approved by the FDA for the treatment of metastatic refractory urothelial cancers, has a safety database that exceeds 2000 patients and has a very well characterized AE profile [57].

[figure not shown]

Figure 4: Distribution of irAEs for anti-PD-L1agents [77]

Distribution of (A) grade 1 to 2 and (B) grade 3 to 5 immune-related adverse events (irAEs) for all tumor types in the main clinical trials with anti-cytotoxic T-cell lymphocyte-4 (anti-CTLA-4), anti-programmed death 1 (PD-1), or anti-PD ligand 1 (PD-L1) antibodies as single therapies. The values quoted are the median (range) irAE rates for the set of clinical trials as a whole.

Table 4: Summary of irAEs in Avelumab Safety Database

irAE	Overall rate %	Grade 3 through 5%	Onset of Symptoms	
			Median	Range
Pneumonitis	1.2	0.5	2.5 months	3 days – 11 months
Hepatitis	0.9	0.5 (grade 3 only)	3.2 months	7 days -15 months
Colitis	1.5	0.4 (grade 3 only)	2.1 months	2 days – 11 months
Adrenal	0.5	0.1 (grade 3 only)	2.5 months	1 day – 8 months
Thyroid	6	0.2 (grade 3 only)	2.8 months	14 days – 13 months
Diabetes	0.1	0.1 (grade 3 only)	NA	NA
Nephritis	0.1	NA	NA	NA

Infusion reaction initially occurred in one quarter of the patients receiving avelumab including 9 patients with grade 3 (0.5%) and 3 patients with grade 4 (0.2%) events that were successfully controlled with antihistamines and IV corticosteroids. The avelumab package insert now recommends routine premedication with an antihistamine during the first 4 infusions. Anti-PD-1 (nivolumab, pembrolizumab or PDR001) antibodies have been given in combination with all versions of rhIL-15, E. coli (NCI produced) single chain agent, heterodimeric IL-15 (Novartis) and the ALT-803 superagonist (Altor now NantKWest). While the number of patients treated with these combinations is still modest, there has not been a new safety signal or evidence of synergistic toxicities. Given the close temporal relationship of CIV rhIL-15 treatment to the transient grade 3 hematologic and occasional metabolic abnormalities, we anticipate that these events will not complicate the recognition of the rare autoimmune events seen with avelumab which would normally become apparent during the second or third cycle of treatment. We believe it is reasonable to use our standard DLT exclusion algorithm even in the initial dose level safety evaluation of patients and will view sustained or delayed grade 3 elevations of liver function tests (LFTs) as DLTs.

2 ELIGIBILITY ASSESSMENT AND ENROLLMENT

2.1 ELIGIBILITY CRITERIA

2.1.1 Inclusion Criteria

2.1.1.1 Patients must have histologically proven metastatic clear cell renal carcinoma with $\geq 5\%$ expression of PD-L1 in the tumor area confirmed by IHC in the NCI Lab of Pathology or performed by an outside CLIA certified laboratory using the FDA licensed Dako 28-8 or

22C3 antibodies PharmDx [79, 80]. Archival tumor sample may be used but if archival tissue is not available or is not adequate, tissue biopsy will be required.

- 2.1.1.2 Patients must have failed or relapsed and have progressive disease after at least 2 prior therapies that include multityrosine kinase inhibitor (mTKI) like axitinib or sunitinib and an anti-PD1 or PD-L1 (ICI) therapy like nivolumab which could have been administered in combination with an anti-CTLA4 agent like ipilimumab. Patients who received an ICI in combination with a mTKI would be eligible for the trial if they received another appropriate treatment. Adjuvant or neoadjuvant with either type of agent would not fulfill this requirement only treatment for metastatic disease will be considered to satisfy this criterion.
- 2.1.1.3 Disease must be measurable with at least one measurable lesion by RECIST v1.1 criteria (see Section 6.3) that is different from the lesion biopsied.
- 2.1.1.4 Age ≥ 18 years

NOTE: Because no dosing or adverse event data are currently available on the use of rhIL-15 in combination with avelumab in patients <18 years of age, children are excluded from this study, but may be eligible for future pediatric trials

- 2.1.1.5 ECOG performance status ≤ 1 (Karnofsky $\geq 80\%$, see APPENDIX A)

- 2.1.1.6 Adequate organ and marrow function as defined below:

absolute neutrophil count	$\geq 1,500/\text{mcL}$
absolute lymphocyte count	$>500/\text{mcL}$
Hemoglobin	$\geq 10 \text{ g/dL}$
Platelets	$\geq 100,000/\text{mcL}$
total bilirubin	$\leq 1.5 \times$ institutional upper limit of normal (ULN)
AST(SGOT)/ALT(SGPT)	$\leq 2.5 \times$ institutional ULN
Serum creatinine	$\leq 1.5 \times$ institutional ULN
OR	
Creatinine clearance	$\geq 50 \text{ mL/min}/1.73 \text{ m}^2$ for patients with creatinine levels >1.5 institutional ULN

- 2.1.1.7 Negative serum or urine pregnancy test at screening for women of childbearing potential (WOCBP).

NOTE: WOCBP is defined as any female who has experienced menarche and who has not undergone successful surgical sterilization or who is not postmenopausal. WOCBP must have a negative pregnancy test (HCG blood or urine) during screening.

- 2.1.1.8 Women of child-bearing potential and men must agree to use adequate contraception (hormonal or barrier method of birth control; abstinence) prior to study entry, for the duration of study participation, and 1 month after completion of rhIL-15 and avelumab administration. Should a woman become pregnant or suspect she is pregnant while she or her partner is participating in this study, she should inform her treating physician immediately.

- 2.1.1.9 Ability of subject to understand and the willingness to sign a written informed consent

document.

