2.3.4 Laboratory Evaluations

NOTE: Results from outside NIH are accepted.

- Hematological Profile: CBC with differential and reticulocyte count
- Biochemical Profile: Creatinine (i.e., Acute Care Panel); serum calcium, phosphate, magnesium and albumin (i.e., Mineral Panel); ALT, AST, total and direct (if required) bilirubin (i.e., Hepatic Panel); 24-hour urine creatinine clearance (if needed to measure CrCl in cases where serum creatinine >1.5mg/dl); and LDH
- Serum Lipase and Amylase
- Coagulation panel, including: PT/INR and a PTT
- Thyroid function tests, including: thyroid stimulating hormone (TSH) and free thyroxine (T4)

- HIV, and hepatitis: Hepatitis B surface antigen (HBsAg), Hepatitis B core antibody, Hepatitis C antibody (HCV) [qualitative], HIV 1/2 antibody (qualitative) **NOTE:** For individuals with a positive hepatitis B core antibody, HBV DNA PCR will be performed to screen for subclinical infection. For individuals with a positive hepatitis C antibody, HCV RNA RT-PCR will be performed to determine infectious status.
- Serum or urine pregnancy test (B-HCG) in women of childbearing potential
- Urinalysis (with microscopic examination if abnormal)
- Antinuclear antibody (ANA), rheumatoid factor (RF) and anti-thyroid antibody
- Creatine phosphokinase (CPK), troponin
- Flow cytometry and lymphocyte sets, and subsets

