Liver test elevation	Initial Management	Follow-up Management
Grade 1 Grade 1 AST or ALT > ULN to 3.0 x ULN and / or total bilirubin > ULN to 1.5 x ULN	Continue avelumab	Continue liver function monitoring If worsens: Treat as Grade 2 or 3 to 4
Grade 2 AST or ALT > 3.0 to \leq 5 x ULN and/or total bilirubin > 1.5 to \leq 3 x ULN	Withhold avelumab Increase frequency of monitoring to every 3 days	If returns to Grade \leq 1: Resume routine monitoring, resume avelumab If elevations persist > 5 to 7 days or worsen: Treat as Grade 3 or 4
Grade 3 to 4 AST or ALT > 5 x ULN and/or total bilirubin > 3 x ULN	Permanently discontinue avelumab Increase frequency of monitoring to every 1 to 2 days 1 to 2 mg/kg/day prednisone or equivalent Add prophylactic antibiotics for opportunistic infections Consult gastroenterologist/ hepatologist Consider obtaining MRI/CT scan of liver and liver biopsy if clinically warranted	If returns to Grade \leq 1: Taper steroids over at least 1 month and add prophylactic antibiotics for opportunistic infections If does not improve in > 3 to 5 days, worsens or rebounds: Add mycophenolate mofetil 1 gram (g) twice daily If no response within an additional 3 to 5 days, consider other immunosuppressants per local guidelines

Table 13: Treatment Modifications for Renal Immune-related AEs

Renal irAEs		
Creatinine Increase	Initial Management	Follow-up Management
Grade 1 Creatinine increased > ULN to 1.5 x ULN	Continue avelumab	Continue renal function monitoring If worsens: Treat as Grade 2 or 3 to 4
Grade 2 to 3 Creatinine increased > 1.5 and \leq 6 x ULN	Withhold avelumab Increase frequency of monitoring to every 3 days 1 to 2 mg/kg/day prednisone or equivalent. Add prophylactic antibiotics for opportunistic infections Consider renal biopsy	If returns to Grade \leq 1: Taper steroids over at least 1 month, and resume avelumab following steroids taper. If worsens: Treat as Grade 4.

Renal irAEs		
Creatinine Increase	Initial Management	Follow-up Management
Grade 4 Creatinine increased > 6 x ULN	Permanently discontinue avelumab Monitor creatinine daily 1 to 2 mg/kg/day prednisone or equivalent. Add prophylactic antibiotics for opportunistic infections Consider renal biopsy Nephrology consult	If improves to Grade \leq 1: Taper steroids over at least 1 month

Table 14: Treatment Modifications for Cardiac Immune-related AEs

Cardiac irAEs		
Myocarditis	Initial Management	Follow-up Management

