3.3.3 Unacceptable Toxicity

Occurrence of any of the adverse events listed in Section [3.1.1](#) after the first 28 days of treatment in the Dose Expansion cohort (Cohort 2) will lead to permanent discontinuation of protocol therapy, but will not be deemed a DLT for purposes of dose escalation. Any patient who requires corticosteroid treatment for an avelumab related irAE will have their rhIL-15 discontinued regardless of their perceived tolerance of the cytokine. Patients may continue single agent avelumab after halting rhIL-15 treatment if considered appropriate in the standard avelumab irAE decision algorithm.

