10.2.1 Early stopping criteria

An early stopping criterion for toxicity for the whole trial itself would be if ≥ 2 of the first 9 or ≥ 4 of the first 17 patients has unacceptable toxicity or an irAE that required discontinuation of avelumab and/or initiation corticosteroid treatment.

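### A patient admitted with creatinine above 1.5 x ULN has no grade 1 row in Table 13: any rise attributed to avelumab leads to the withhold-and-prednisone row, and the resumption level lies below the patient's own entry value

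*Combined protocol and SAP*

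**What the plan says.** **Entry.** Section 2.1.1.6 asks for serum creatinine of at most 1.5 x ULN or, as the alternative, a clearance of at least 50 mL/min/1.73 m² "for patients with creatinine levels >1.5 institutional ULN". The alternative has no creatinine ceiling.

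**On treatment.** Table 13 in 3.3.2.2 has three rows, all defined by ULN:
- Grade 1, "Creatinine increased > ULN to 1.5 x ULN": avelumab continues.
- The next row, "Grade 2 to 3 Creatinine increased > 1.5 and" up to 6 x ULN: "Withhold avelumab Increase frequency of monitoring to every 3 days 1 to 2 mg/kg/day prednisone or equivalent". Avelumab resumes after the steroid taper if creatinine returns to grade 1 or lower.
- Grade 4, above 6 x ULN: avelumab is stopped permanently.

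**What steroids set off.** Section 3.3.3 states: "Any patient who requires corticosteroid treatment for an avelumab related irAE will have their rhIL-15 discontinued". Section 3.1 makes an irAE needing corticosteroids in cycle 1 a DLT for the run-in cohort. Section 10.2.1 stops the trial for toxicity at 2 or more of the first 9, or 4 or more of the first 17, counting unacceptable toxicity or "an irAE that required discontinuation of avelumab and/or initiation corticosteroid treatment".

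**Measuring clearance.** Sections 2.3.4 and 2.5.2 call for a 24-hour collection at a fixed creatinine value; in 2.3.4 the words are "if needed to measure CrCl in cases where serum creatinine >1.5mg/dl".

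**The concern.** The entry criterion and the toxicity table meet at the same number, 1.5 x ULN, but from opposite sides. The clearance route admits only patients above it, and Table 13 begins its withhold-and-steroid row just above it. Because the table does not refer to baseline, it cannot separate a large rise in a patient who entered with normal creatinine from a trivial rise in a patient who entered above 1.5 x ULN.

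This is foreseeable. The trial is in renal cancer, it deliberately provides a route for raised creatinine, and increased creatinine is listed as a possible effect of both rhIL-15 (14.1.8) and avelumab (14.2.2). Once a small rise is attributed to avelumab, the consequences run beyond that patient's treatment. The same event enters the DLT count and the whole-trial stopping count, both of which act on very few events.

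**Working it through.** No stated figure has to be reproduced here; the check is a comparison of thresholds.

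**1. Entry limits against the Table 12 and 13 rows**

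| Test | Entry limit (2.1.1.6) | Grade 1 row, avelumab continues | Highest admitted value inside grade 1? |
|---|---|---|---|
| AST/ALT | at most 2.5 x ULN | up to 3.0 x ULN | yes |
| Bilirubin | at most 1.5 x ULN | up to 1.5 x ULN | yes |
| Creatinine, first route | at most 1.5 x ULN | up to 1.5 x ULN | yes |
| Creatinine, clearance route | above 1.5 x ULN, no ceiling | up to 1.5 x ULN | no |

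Only the clearance route admits patients above grade 1. The liver-test exception to the DLT definition (3.1.1.2) also has a clause relative to baseline; creatinine has none.

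**2. What the rows do to a small rise (hypothetical values)**

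- Patient A enters at 1.6 x ULN and rises to 1.7 x ULN. The change is 0.1/1.6 = 6%. The row reached is withhold and prednisone.
- Patient B enters at 1.0 x ULN and must rise by more than 0.5/1.0 = 50% to reach the same row.
- To resume, A must fall to 1.5 x ULN, which is 0.1/1.6 = 6% below A's own entry value. B need only return to 50% above entry.

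**3. Can such a patient be enrolled?** The documents give no ULN, so 1.0 to 1.4 mg/dl is assumed. As a proxy for the 24-hour collection, take Cockcroft-Gault for a man, (140 − age) x weight / (72 x creatinine), scaled by 1.73/BSA with BSA = √(height x weight/3600). Creatinine is set at 1.51 x ULN.

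- Age 45, 90 kg, 178 cm: BSA = 2.11. At ULN 1.0, 95 x 90/(72 x 1.51) = 78.6, scaled to 64.5. At ULN 1.2, 1.3 and 1.4 the scaled values are 53.7, 49.6 and 46.1.
- Age 60, 80 kg, 175 cm: scaled values of 51.6, 46.9 and 43.0 at ULN 1.0, 1.1 and 1.2.

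Against the limit of 50, the overlap exists but is narrow: mainly younger or larger patients just above 1.5 x ULN, at the lower assumed ULNs.

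**4. What one counted event does.** This is conditional on one such patient being counted and says nothing about how often that happens. Assume every other patient has a counted event with probability q of 5% to 10% (not in the documents).

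- First 9, nobody pre-counted: 1 − (1−q)^9 − 9q(1−q)^8 = 7% (q = 5%) or 23% (q = 10%).
- First 9, one already counted: 1 − (1−q)^8 = 34% or 57%.
- Run-in level of 6, at least 2 DLTs: 3% or 11% with nobody pre-counted, against 1 − (1−q)^5 = 23% or 41% with one already counted.

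Any single counted event has this effect. The figures show only why the definition of an event matters at these sample sizes.

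**5. Clearance trigger.** 1.5 x ULN equals 1.5 mg/dl only when ULN is 1.0 mg/dl. For ULN of 0.9 to 1.3 it is 1.35 to 1.95 mg/dl. Above 1.0, the laboratory trigger reaches patients who do not need a clearance for eligibility. Below 1.0, a patient between 1.5 x ULN and 1.5 mg/dl needs one but does not meet the trigger.

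**The case against.** The strongest reply is that Table 13 concerns immune-related events and a creatinine increase, so a stable value is neither. That is right. Section 8.1.1 ties an adverse event to use of the product, 6.1.1 records events from the first study intervention, and avelumab is first given on day 8. A reader might infer that a patient enrolled above 1.5 x ULN is already in the row on day 1; the documents do not support that.

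Three other inferences also fail.
- Such a patient does not lose both drugs in cycle 1. The rhIL-15 infusion of days 1 to 5 is over before the first avelumab dose, the row says withhold rather than stop, and 3.3.3 allows single-agent avelumab after rhIL-15 ends where the irAE algorithm permits.
- Section 10.2.1 does not allow two events in the first 9 patients. It tolerates one.
- No loss of power or overall stopping probability can be calculated, because the share of patients entering by this route is not given. Nor is response automatically lost: under 10.3.2, patients who discontinue are set to non-response if they are not restaged.

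Exclusion 2.1.2.15 lets the investigator decline a patient whose laboratory abnormalities raise risk or could obscure the results. Exclusion 2.1.2.2 limits persisting toxicity of prior therapy. Both help, but both rest on judgement or cause, and neither removes the clearance route.

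What the reply does not answer is a small rise during treatment that is attributed to avelumab. That is an increase, it lies in the row, and no text separates trivial from real change. Section 6.1.2.1 restricts which laboratory values are adverse events, but one of its conditions is that treatment is required, and the row itself prescribes treatment.

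**Conclusion.** The concern holds for one defined situation: a patient enrolled through the clearance route whose creatinine then rises by any amount and whose rise is attributed to avelumab. For that patient Table 13 as written offers no grade 1 step and sets a resumption level below the entry value. The resulting steroid treatment ends rhIL-15 and feeds the run-in DLT count and the 10.2.1 count. This is a contradiction between entry criterion and toxicity table, not merely missing detail, because the rows give a definite and unintended answer for an eligible patient.

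Its size cannot be derived from the documents. The clearance illustration suggests few patients, and it rests on assumed ULNs, assumed body sizes and an estimate standing in for a measured clearance. The conditional figures rest on an assumed 5% to 10% event rate in the other patients and are not a forecast. The mismatch in the clearance trigger is separate and minor.

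**What to change.** - Reconcile 2.1.1.6 with Table 13, covering both the grade rows and the resumption level, so that they are consistent for a patient whose baseline creatinine is above 1.5 x ULN. Which reference and which threshold to use is for the investigators.
- Carry the reconciled definition of a renal irAE into the DLT text in 3.1 and the stopping criterion in 10.2.1, so that all three count the same event.
- State the same trigger for measuring clearance in 2.1.1.6, 2.3.4 and 2.5.2.

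The cost is protocol wording in an amendment. Baseline creatinine is already collected under 2.5.2, so no new data, visits or patients are needed.
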